10.3.6. Clinical laboratory parameters and other abnormal assessments qualifying as AEs or SAEs

In the absence of a diagnosis, abnormal laboratory findings (e.g. clinical chemistry, hematology, urinalysis) or other abnormal assessments the investigator considers clinically significant will be recorded as an AE or SAE if they meet the definition of an AE or SAE (refer to the Sections 10.3.1 and 10.3.2).

The investigator will exercise his or her medical and scientific judgment in deciding whether an abnormal laboratory finding or other abnormal assessment is clinically significant.

10.3.7. Events or outcomes not qualifying as AEs or SAEs

10.3.7.1. **Pregnancy**

This section is not applicable for the study population.

10.3.8. Recording and follow-up of AEs, SAEs and pIMDs (Amended: 01 April 2022)

The participants will be instructed to contact the investigator immediately should they manifest any signs or symptoms they perceive as serious.

When an AE/SAE occurs, it is the responsibility of the investigator to review all documentation (e.g. hospital progress notes, laboratory and diagnostics reports) relative to the event. The investigator will then record all relevant information regarding an AE/SAE in the eCRF. The investigator is not allowed to send photocopies of the participant's medical records to GSK instead of appropriately completing the eCRF. However, there may be instances when copies of medical records for certain cases are requested by GSK. In this instance, all participant identifiers will be blinded on the copies of the medical records prior to submission to GSK.

The investigator will attempt to establish a diagnosis pertaining to the event based on signs, symptoms, and/or other clinical information. In such cases, the diagnosis should be documented as the AE/SAE and not the individual signs/symptoms.

A Paper Diary, hereafter referred to as Participant Diary will be used in this study to capture solicited administration site or systemic events and unsolicited AEs. The participant should be trained on how and when to complete each field of the Participant Diary. If a participant is unable or not willing to complete the paper diary him/herself, he/she may be helped by a caregiver (refer to the Glossary of terms for the definition of caregiver).

212496 (RSV OA=ADJ-004) Protocol Amendment 1 Final

Any individual(s) who performs the measurements of administration site or systemic events and who will enter the information into the Participant Diary should be trained on the use of the Diary; for example, the study caregiver should have received a caregiver information letter explaining the role of the caregiver prior to completing the diary card. This training must be documented in the participant's source record. If any other individual than the participant is making entries in the Participant Diary (i.e., caregiver), their identity should be documented in the participant's source record.

- Collect and verify completed diary cards during discussion with the participant at Day 31 for all groups, and at Month 13 *for the RSV_annual group only* and Month 25 for the RSV_annual *and RSV_flexible revaccination* groups.
- Any unreturned diary cards will be sought from the participant through telephone call(s) or any other convenient procedure.

The investigator or designee will transcribe the required information into the eCRF in English. Refer to the SPM for more information regarding the completion of the paper diary.

10.3.8.1. Time period for collecting and recording AEs, SAEs and pIMDs

All solicited administration site and systemic events that occur during 4 days following administration of each dose of study vaccine must be recorded into the appropriate section of the eCRF, irrespective of intensity. All unsolicited AEs that occur during 30 days following administration of each dose of study vaccine must be recorded into the appropriate section of the eCRF, irrespective of intensity or whether or not they are considered vaccination-related.

The time period for collecting and recording SAEs and pIMDs will begin at the first receipt of study vaccine and will end 6 months after study vaccine administration.

All SAEs and pIMDs considered related to study vaccination, any fatal SAEs and AEs/SAEs leading to withdrawal from the study will be collected and recorded from the time of the first receipt of study vaccine until the participant is discharged from the study. SAEs related to study participation or to a concurrent GSK medication/vaccine will be collected from the time consent is obtained until the participant is discharged from the study.

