7.1.2. Contraindications to subsequent vaccine administration (Amended: 01 April 2022)

Participants in the RSV_annual *and RSV_flexible revaccination* groups must be evaluated to confirm they are eligible for subsequent vaccination before administering each additional study vaccine dose.

Participants who meet any of the criteria listed below or criteria listed in Sections 5.2.1 and 5.2.2 should not receive additional vaccinations. However, these participants should be encouraged to continue other study procedures at the discretion of the investigator (Section 10.3.8.2). The relevant criteria for discontinuing vaccination must be recorded in the eCRF.

- Participants who experience any SAE judged to be possibly or probably related to study vaccine or non-study vaccines, including hypersensitivity reactions.
- Participants who develop any new condition which, in the opinion of the investigator, may pose additional risk to the participant if he/she continues to participate in the study.
- Anaphylaxis following the administration of vaccine.
- Any condition that in the judgment of the investigator would make intramuscular injection unsafe.
- Occurrence of a new pIMD or the exacerbation of an existing pIMD that, in the opinion of the investigator, exposes the participant to unacceptable risk from subsequent vaccination. In such cases, the investigator should use his/her clinical judgment prior to administering the next dose of the vaccine. Refer to Section 10.3.5 for the definition of pIMDs.

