8.2. Safety Assessments

The investigator and any designees are responsible for detecting, documenting, and reporting events that meet the definition of an AE or SAE. The investigator and any designees remain responsible for following up AEs that are serious, considered related to the study intervention or the study, or that caused the participant to discontinue the study intervention or study.

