8.3. AEs, SAEs and other events of interest

8.3.1. Time period and frequency for collecting AE, SAE and other safety information

An overview of the protocol-required reporting periods for AEs, SAEs and pIMDs is given in Table 14.

Table 14 Timeframes for collecting and reporting of safety information

	Pre- Dose 1*	Dose 1**			6 months after	Revaccination Year 1 (Month 12)** Revaccination Year 2 (Month 24)**				Study Conclusion				
	D1	D1	D4	D30	vaccination (M6)	M12	M12 + D4	M13	M18	M24	M24 + D4	M25	M30	(M36)
Solicited administration site and systemic events														
Unsolicited AEs														
All SAEs/pIMDs														
SAEs/pIMDs related to study vaccination														
SAEs related to study participation or concurrent GSK medication/vaccine														
Fatal SAEs														
AEs/SAEs leading to withdrawal from the study														
Intercurrent medical conditions														

D = day; M = month; Vacc = vaccination; AE = adverse event; SAE = serious adverse event; pIMD = potential immune-mediated disease

01 April 2022 55

^{*}i.e. consent obtained on Day 1 (prior to vaccination).

^{**}Solicited administration site and systemic events up to 4 days, unsolicited AEs up to 30 days and SAEs/pIMDs up to 6 months will be collected only after vaccination.

Note: COVID-19 cases will be collected during the same timeframes as those used for collecting and reporting the other safety information (unsolicited AEs/SAEs, etc.).

212496 (RSV OA=ADJ-004) Protocol Amendment 1 Final

The investigator or designee will record and immediately report all SAEs to the sponsor or designee via the Expedited AE Reporting Form. This reporting should, under no circumstances, occur later than 24 hours after the investigator becomes aware of an SAE, as indicated in Section 10.3.10. The investigator will submit any updated SAE data to the sponsor within 24 hours of it being available.

A post-study AE/SAE is defined as any event that occurs outside of the AE/SAE reporting periods defined in Table 14. Investigators are not obligated to actively seek AEs or SAEs in former study participants. However, if the investigator learns of any SAE, including a death, at any time after a participant has been discharged from the study, and he/she considers the event to be reasonably related to the study vaccine, the investigator will promptly notify the Study Contact for Reporting SAEs mentioned in the Table 16.

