- The number and percentage of participants with any unsolicited AEs during the 30-day follow-up period (i.e., on the day of vaccination and 29 subsequent days) with its exact 95% CI will be tabulated for each dose by group and by Medical Dictionary for Regulatory Activities (MedDRA) *Primary System Organ Class* (SOC), High Level Term (HLT) and Preferred Term (PT). Similar tabulation will be done for Grade 3 unsolicited AEs, for any causally related unsolicited AEs, for Grade 3 causally related unsolicited AEs and for unsolicited AEs resulting in a medically attended visit. The verbatim reports of unsolicited AEs will be reviewed by a qualified person and the signs and symptoms will be coded according to the MedDRA Dictionary for Adverse Reaction Terminology. Every verbatim term will be matched with the appropriate Preferred Term.
- The number and percentage of participants with at least one report of SAE classified by the MedDRA *Primary SOC*, *HLT and* PTs and reported from Dose 1 up to 6 months post-Dose 1 and from revaccination dose up to 6 months post-revaccination will be tabulated with exact 95% CI.
- The number and percentage of participants with at least one report of causally related SAE classified by the MedDRA *Primary SOC*, *HLT and* PTs and reported during the entire study period will be tabulated with exact 95% CI.
- The same tabulation will be presented for fatal SAEs.
- All SAEs will also be described in detail *in a tabular listing*.
- All AEs/SAEs leading to study/intervention discontinuation from Dose 1 up to study end will be tabulated.
- The number and percentage of participants with at least one report of pIMD classified by the MedDRA *Primary SOC*, *HLT and* PTs and reported from Dose 1 up to 6 months post-primary and from revaccination dose up to 6 months post-revaccination will be tabulated with exact 95% CI.
- The number and percentage of participants with at least one causally related pIMD classified by the MedDRA *Primary SOC*, *HLT and* PTs and reported during the entire study period will be tabulated with exact 95% CI.
- All pIMDs will also be described in detail *in a tabular listing*.
- The analyses of unsolicited AEs will include SAEs (unless otherwise specified).

The analysis of safety will also be performed by age category (age at Dose $1: \ge 65$ YOA, ≥ 70 YOA, ≥ 80 YOA, 60-69 YOA and 70-79 YOA) and region (North America, Europe, Asia).

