- The number and percentage of participants with at least one report of SAE classified by the MedDRA Primary SOC, HLT and PTs and reported from Dose 1 up to 6 months post-Dose 1 and from revaccination dose up to 6 months post-revaccination will be tabulated with exact 95% CI. The same tabulation will be presented for causally related SAEs and fatal SAEs,.
- The number and percentage of participants with at least one report of causally related SAEs classified by the MedDRA Primary SOC, HLT and PTs will be reported after each dose and from Day 1 up to study end with exact 95% CI. The same tabulation will be presented for fatal SAEs.
- All SAEs will also be described in detail in a tabular listing.
- All AEs/SAEs leading to study/intervention discontinuation from dose 1 up to study end will be tabulated.
- The number and percentage of participants with at least one report of pIMD classified by the MedDRA Primary SOC, HLT and PTs and reported from Dose 1 up to 6 months post-Dose 1 and from revaccination dose up to 6 months post-revaccination will be tabulated with exact 95% CI. The same tabulation will be presented for causally related pIMDs
- The number and percentage of participants with at least one causally related pIMD classified by the MedDRA Primary SOC, HLT and PTs will be reported after each dose and from Day 1 up to study end with exact 95% CI.
- All pIMDs will also be described in detail in a tabular listing.
- The analyses of unsolicited AEs will include SAEs (unless otherwise specified).

The analysis of safety will also be performed by age category (age at Dose $1: \ge 65$ YOA, ≥ 70 YOA, ≥ 80 YOA, 60-69 YOA and 70-79 YOA) and region (North America, Europe, Asia).

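### An AE that cancels a revaccination dose may have no required AE record, although the protocol and SAP tabulate all such AEs to study end

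*Protocol*

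**What the plan says.** **Collection.** Protocol 10.3.8.1 sets three periods.
- For non-serious events: "All unsolicited AEs that occur during 30 days following administration of each dose of study vaccine must be recorded".
- For SAEs and pIMDs in general, collection "will end 6 months after study vaccine administration". Footnotes to Tables 1 and 2 confine the recording of any SAE or pIMD to those 6-month periods.
- To discharge: related SAEs and pIMDs, and "any fatal SAEs and AEs/SAEs leading to withdrawal from the study will be collected and recorded". SAEs related to study participation or to a concurrent sponsor product are also collected throughout.

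The last row type appears in Table 14 as "AEs/SAEs leading to withdrawal from the study", and in the same terms in the schedules of activities.

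**Analysis.** Protocol 9.4.4.3 states: "All AEs/SAEs leading to study/intervention discontinuation from Dose 1 up to study end will be tabulated". SAP Amendment 3, section 5.4.4, repeats this: "All AEs/SAEs leading to study/intervention discontinuation from dose 1 up to study end will be tabulated".

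**Stopping the vaccine is not leaving the study.** Section 7.1 allows a participant who misses a planned dose to continue other procedures. Section 7.1.2 says of participants who meet a contraindication that "these participants should be encouraged to continue other study procedures at the discretion of the investigator". Section 8.2 makes the investigator responsible for following up AEs that are serious, related, "or that caused the participant to discontinue the study intervention or study".

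**The concern.** The table covers two kinds of event: those that end study participation and those that end vaccination. The to-study-end collection category covers only the first. A participant can lose a revaccination dose to an AE and remain in follow-up. If that AE began outside the 30-day or 6-month window, no collection rule requires it to be entered as an AE.

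An example built from the protocol's own lists: a malignancy is diagnosed at Month 9, is judged unrelated, is not fatal, and the participant stays in the study. Section 7.1.2 refers back to the conditions in 5.2.1, which mention current malignancy, so the next dose is not given. Section 10.3.2 gives malignant cancer as an example of a serious event. Month 9 is more than 6 months after Dose 1, so the event falls under none of the collection categories.

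Safety of each vaccination schedule is a secondary objective, and events that prevent revaccination bear on it. The gap could also be misread. Protocol 9.4.1.3 and SAP 5.1.3 count a participant with no reported event as a participant without the event, so an uncollected AE would look like an absent one.

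**Working it through.** There is no plan figure to reproduce. The check compares the categories and then measures the time outside the windows.

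**Step 1. Which events that cancel a dose, without ending participation, must be entered as an AE or SAE?**

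| Event | Required collection period |
|---|---|
| Related SAE or related pIMD | First dose to discharge |
| Fatal SAE | First dose to discharge (no later dose arises) |
| Unrelated non-fatal SAE, or unrelated pIMD | 6 months after each dose |
| Other non-serious AE | 30 days after each dose |

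Only the last two rows leave a gap.

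**Step 2. Which groups are affected?** RSV_annual (~990) has doses to lose at Months 12 and 24, and RSV_flexible (~330) at Month 24. RSV_1dose has no later dose and is unaffected. After Month 24 no planned dose remains, so the relevant period is Dose 1 to Month 24.

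**Step 3. How much of that period is uncovered?** Inputs: intervals of 365 and 730 days (Tables 4 and 5), a 30-day AE window, and 6 months taken as 180 days, the length in those tables. The Month 12 dose is assumed given in RSV_annual. Uncovered days per interval = interval − window.

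| | RSV_annual, two intervals | RSV_flexible, one interval |
|---|---|---|
| Non-serious AEs | 2 × (365 − 30) = 670 | 730 − 30 = 700 |
| Unrelated non-fatal SAEs, unrelated pIMDs | 2 × (365 − 180) = 370 | 730 − 180 = 550 |

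As shares of a single dose-to-dose interval:
- Non-serious AEs: 335/365 = 91.8% and 700/730 = 95.9%.
- Unrelated non-fatal SAEs and unrelated pIMDs: 185/365 = 50.7% and 550/730 = 75.3%.

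**Step 4. Sensitivity to visit timing.** Over the allowed intervals (350–380 and 715–745 days), the AE shares are 91.4–92.1% and 95.8–96.0%. The SAE/pIMD shares are 48.6–52.6% and 74.8–75.8%. If the 6-month contact falls at the 210-day limit and collection runs to it, the SAE/pIMD days become 2 × (365 − 210) = 310 and 730 − 210 = 520.

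All of these are amounts of time. The documents give no rate of AE-driven dose discontinuation and no onset distribution, so they cannot be turned into a number of missing events.

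**The case against.** The best reply is that these participants are not lost from view.
- Section 7.1 requires the primary reason for stopping the intervention in the eCRF, with three AE categories among the options.
- Section 7.1.2 requires the contraindication criterion in the eCRF.
- The schedules carry a row for intercurrent medical conditions. It points to 9.3.1.1, which refers to the 7.1.2 criteria.
- Section 8.2 gives the investigator a duty to document AEs and to follow those that stopped the intervention.
- The eCRF and the Study Procedures Manual are not among the documents and may ask for more.

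All of that stands as evidence that the discontinuation, and roughly its cause, will be known. None of it requires an AE record with term, onset, intensity, causality and outcome. Section 9.3.1.1 serves per-protocol elimination. Follow-up under 10.3.8.2 begins after an initial report, which is not required outside the windows.

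It is also fair that the gap is confined to late-onset events that are non-serious, or unrelated and non-fatal, and that the table is not a listed endpoint. The defined safety endpoints match the collection periods.

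A reader might infer from the 92% and 96% that AEs stopping revaccination mostly go uncollected and that the table is certain to undercount. The documents do not support that. The percentages are shares of time, and they become shares of events only if onset is uniform. Some stopping criteria, such as anaphylaxis after vaccination, arise soon after a dose, and related SAEs and pIMDs are collected throughout.

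A reader might also infer that the two revaccination groups cannot be compared on this row. For non-serious AEs, 670 against 700 days is near parity. Only the unrelated non-fatal SAE and unrelated pIMD time differs materially, the groups have different numbers of doses to miss, and the trial is descriptive.

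**Conclusion.** The collection rule is narrower than the table built on it, and it conflicts with the follow-up duty in 8.2. Followed as written, the plan can leave the intervention-discontinuation part of the table incomplete in RSV_annual and RSV_flexible. The affected events are non-serious AEs starting more than 30 days after a dose, and unrelated non-fatal SAEs or unrelated pIMDs starting more than 6 months after a dose, in participants who stay in the study.

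The exposure to Month 24 is the uncovered time in the working above, on nominal visit timing with 6 months taken as 180 days. The resulting shortfall in events cannot be sized and could be nil if sites record these AEs anyway. The inconsistency should be corrected, but it does not undermine the defined safety endpoints.

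**What to change.** In protocol 10.3.8.1, Table 14 and the matching rows of Tables 1 and 2, widen the existing category so that it covers AEs/SAEs leading either to study withdrawal or to discontinuation of the study intervention, collected from Dose 1 to study end. Require an AE or SAE record linked to the discontinuation-reason page whenever the reason given is an AE.

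For doses already missed for an AE, query the site once for the event. Where that is not possible, footnote the table with its data source and the period in which collection was incomplete.

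The cost is a small eCRF change and a few site queries. No visit, procedure or dosing rule changes.

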10.3.8.2. Follow-up of AEs, SAEs, pIMDs or any other events of interest

After the initial report of an AE/SAE/pIMD or any other event of interest for the study, the investigator is required to proactively follow each participant at subsequent visits/contacts. All SAEs and pIMDs (as defined in the Section 10.3.5), will be followed until the event is resolved, stabilized, otherwise explained, or the participant is lost to follow-up.

Refer to Section 10.3.10 for timeframes and further information on how to report SAEs, pIMDs and other events.

10.3.8.2.1. Follow-up during the study

AEs (serious or non-serious) or pIMDs documented at a previous visit/contact and defined as not recovered/not resolved or recovering/resolving will be reviewed at subsequent visits/contact until the end of the study or the participant is lost to follow-up.

If participant dies during participation in the study or during a recognized follow-up period, GSK will be provided with any available post-mortem findings, including histopathology.

10.3.8.2.2. Follow-up after the participant is discharged from the study

The investigator will provide any new or updated relevant information on previously reported SAE/pIMD to GSK using a paper/electronic Expedited Adverse Events Report as applicable. The investigator is obliged to perform or arrange for the conduct of supplemental clinical examinations/tests and/or evaluations to elucidate the nature and/or causality of the AE or SAE as fully as possible.

10.3.8.3. Updating of SAE and pIMD information after removal of write access to the participant's eCRF

When additional SAE or pIMD information is received after removal of write access to the participant's eCRF, new or updated information should be recorded on the appropriate paper report, with all changes signed and dated by the investigator. The updated report should be faxed to the Study Contact for Reporting SAEs (refer to the Section 8.3.3.1 or to GSK Clinical Safety and Pharmacovigilance department within the defined reporting timeframes specified in the Table 15.

10.3.9. Assessment of intensity and toxicity

10.3.9.1. Assessment of intensity

The intensity of the following solicited events will be assessed as described:

Table 28 Intensity scales for solicited events in adults

Adults		
Event	Intensity grade	Parameter
Pain at administration site	0	None
	1	Mild: Any pain neither interfering with nor preventing normal everyday activities.
	2	Moderate: Painful when limb is moved and interferes with everyday activities.
	3	Severe: Significant pain at rest. Prevents normal everyday activities.
Erythema at administration site		Record greatest surface diameter in mm
Swelling at administration site		Record greatest surface diameter in mm
Temperature*		Record temperature in °C/°F (with 1 decimal)
Headache	0	Normal
	1	Mild: Headache that is easily tolerated
	2	Moderate: Headache that interferes with normal activity
	3	Severe: Headache that prevents normal activity
Fatigue	0	Normal
	1	Mild: Fatigue that is easily tolerated
	2	Moderate: Fatigue that interferes with normal activity
	3	Severe: Fatigue that prevents normal activity
Myalgia	0	Normal
	1	Mild: Myalgia that is easily tolerated
	2	Moderate: Myalgia that interferes with normal activity
	3	Severe: Myalgia that prevents normal activity
Arthralgia	0	Normal
	1	Mild: Arthralgia that is easily tolerated
	2	Moderate: Arthralgia that interferes with normal activity
* D. C. 1. O. 1 4.0 C. II 1 C. 11	3	Severe: Arthralgia that prevents normal activity

^{*} Refer to Section 1.3 for the definition of fever and the preferred location for temperature measurement.

The maximum intensity of local administration site erythema/swelling and fever will be scored at GSK as follows:

	Erythema/swelling	Fever
0:	≤ 20 mm	< 38.0°C (100.4°F)
1:	> 20 - ≤ 50 mm	≥ 38.0°C (100.4°F) - ≤ 38.5°C (101.3°F)
2:	> 50 - ≤ 100 mm	> 38.5°C (101.3°F) - ≤ 39.0°C (102.2°F)
3:	> 100 mm	> 39.0°C (102.2°F)

The investigator will assess the maximum intensity that occurred over the duration of the event for all unsolicited AEs (including SAEs) recorded during the study. The assessment will be based on the investigator's clinical judgment.

212496 (RSV OA=ADJ-004) Protocol Amendment 1 Final

The intensity should be assigned to 1 of the following categories:

1 (mild) = An AE which is easily tolerated by the participant, causing minimal discomfort and not interfering with everyday activities.

2 (moderate) = An AE which is sufficiently discomforting to interfere with

normal everyday activities.

3 (severe) = An AE which prevents normal, everyday activities.

Such an AE would, for example, prevent attendance at work and would necessitate the administration of corrective therapy.

An AE that is assessed as Grade 3 (severe) should not be confused with an SAE. Grade 3 is a category used for rating the intensity of an event; and both AEs and SAEs can be assessed as Grade 3. An event is defined as 'serious' when it meets 1 of the pre-defined outcomes as described in the Section 10.3.2.

